## 4.2 Exclusion Criteria

- 4.2.1 Current or planned use (within the study period) of any of the following agents, as requested by the Gilead Sciences clinical pharmacology team:

Anticonvulsants: Phenobarbital, Phenytoin, Carbamazepine, Oxcarbazepine  
Antimycobacterial: Rifampin, rifapentine  
Herbal Products: St. John’s wort, Echinacea  
Antiarrhythmic Agents: Dofetilide  
GI Motility Agents: Cisapride  
ART: Atazanavir

- 4.2.2 Change or initiation of lipid- and/or glucose-lowering therapy in the 12 weeks prior to entry, or planned need for such therapy during the study period. Use of stable lipid- and/or glucose-lowering therapy during the study is allowed.

- 4.2.3 Current use of androgen therapy.

- 4.2.4 Intent to significantly modify diet or exercise habits, or to enroll in a weight loss intervention during the study period.

- 4.2.5 Anticipated need to initiate or change doses of medications with anti-inflammatory properties within the study period.

- 4.2.6 Screening laboratory values as follows:

ANC <500 cells/mm^3  
Hemoglobin <10 gm/dL  
Cr Cl <30 mL/min (estimated by CKD-Epi equation)  
AST or ALT >3x ULN

- 4.2.9 Evidence of resistance to any component of a subject’s current ART regimen (genotypic or phenotypic), with the exception that isolated M184V is not exclusionary.

4.2.10 Current use of bictegravir in another investigational setting.

4.2.11 Current use of other investigational agents that the participant could not receive unchanged, if needed, throughout the study period (unless approved by the study team).

4.2.12 Any condition that the study investigator believes would make the candidate unsuitable for participation.

## **5.0 Study Treatment**

### **5.1 Regimens, Administration, and Duration**

Study treatment is open label bictegravir + tenofovir alafenamide + emtricitabine (only bictegravir is investigational).

At entry participants will be randomized 1:1 by the study team to:

ARM A (immediate switch): Switch current ART to bictegravir + tenofovir alafenamide + emtricitabine for 48 weeks

or

ARM B (no switch): Continue current therapy for 48 weeks

If randomized to ARM A at study entry, the subject will substitute bictegravir + tenofovir alafenamide + emtricitabine for their entry ART regimen.

### **5.2 Study Product Formulation and Preparation**

To be provided by manufacturer.

### **5.3 Pharmacy: Product Acquisition, Distribution, and Accountability**

#### Study Product Acquisition/Distribution

Bictegravir + tenofovir alafenamide + emtricitabine will be supplied by Gilead Sciences. Participants randomized to Arm B will obtain ART for the study period through the usual means. Bictegravir + tenofovir alafenamide + emtricitabine is commercially available, so participants can receive bictegravir + tenofovir alafenamide + emtricitabine through usual care if they decide to continue it after the 48-week study period.

### **5.4 Concomitant Medications**

#### Prohibited Medications

The prohibited medications are:

Anticonvulsants: Phenobarbital, Phenytoin, Carbamazepine, Oxcarbazepine

Antimycobacterial: Rifampin, rifapentine

Herbal Products: St. John's wort, Echinacea

Antiarrhythmic Agents: Dofetilide

GI Motility Agents: Cisapride

ART: Atazanavir

#### Precautionary Medications

Use of antacids must be timed to be  $\geq 2$  hours from the timing of bictegravir + tenofovir alafenamide + emtricitabine dosing.

## 6.0 Clinical Evaluations

### 6.1 Schedule of Events

	Screen	Baseline*	Week 4	Week 12	Week 24*	Week 36	Week 48*	Early Discontinuation
Demographics	X							
Hormone therapy questionnaires		X						
Medical and medication history	X							
Targeted physical exam with weight, vital signs		X	X	X	X	X	X	
Complete physical exam and height	X							
DXA for bone mineral density, lean and fat mass		X					X	X
FibroScan for hepatic steatosis and fibrosis assessment		X					X	X
HIV-1 RNA	X		X	X	X		X	X
Safety labs**	X	X	X	X			X	X
CD4 + T lymphocyte count		X		X	X		X	X
Fasting lipids, banked serum and plasma samples for insulin and biomarkers		X			X		X	X
Medication dispensation		X	X	X	X	X		

\* Entry, week 24 and week 48 laboratory evaluations are required to be fasting (at least 8 hours)

\*\*Safety labs include: CBC with differential, chemistry panel including liver enzymes (ALT, AST, Alk Phos), total bilirubin and serum creatinine. All safety labs, HIV-1 RNA, and CD4+ T lymphocyte counts will be performed at local certified laboratories.

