### Visit 2 Baseline (within 45 days of screening)

Once eligibility has been confirmed, the subject will be randomized 1: 1 to either:

ARM A: Immediate switch of current ART to bictegravir + tenofovir alafenamide + emtricitabine for 48 weeks.  
or

ARM B: Continue current ART unchanged for 48 weeks.

Visit windows for all subsequent visits will be +/- 14 days from the expected date.

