## **6.6. Laboratory Evaluations**

Fasting will be required for study entry and weeks 24 and 48. Fasting will be defined as nothing by mouth except water and medications for at least 8 hours prior to the lab draw. At screening and entry, all laboratory values, regardless of grade, must be recorded on the CRFs. For post-entry assessments, record all laboratory values for WBC, Hb, platelet, glucose, creatinine, AST, ALT, lipid profile, CD4+ T lymphocyte count and HIV-1 RNA, and any other  $\geq$  Grade 2 laboratory value. Any laboratory value leading to a change in ART treatment must be recorded regardless of grade. Fasting lab studies include: total cholesterol, LDL cholesterol, triglycerides, HDL cholesterol, glucose (at weeks 0, 24 or 48), insulin and all biomarker measurements.

The site must refer to the Division of AIDS Table for Grading the Severity of Adult and Pediatric Adverse Events (DAIDS AE Grading Table), Version 2.0, November 2014, which is available on site.

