## **7.0 Toxicity Management**

Criteria for participant management, dose interruptions, modifications, and discontinuation of drug treatment will be mandated only for toxicities attributable to study drug (for Arm A participants). Toxicities due to drugs in the background regimen/entry regimen (for Arm B participants) should be managed according to standard clinical practice, with the goal of maintaining continuous therapy, if possible.

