### **7.2 Grade 3 Toxicity**

Participants who develop a Grade 3 AE or toxicity should have all antiretroviral medications, including study drug, withheld unless the investigator has compelling evidence that the AE has NOT been caused by the study drug. The study chair ([name]) should be notified of any Grade 3 or greater toxicity. The subject should be re-evaluated closely until the AE returns to Grade  $\leq 2$ , at which time study drug may be reintroduced at the discretion of [name] or according to standard practice.

If the same Grade 3 AE recurs within 4 weeks following reintroduction and it is thought to be related possibly, probably, or definitely to study drug, then study drug must be permanently discontinued. If the same Grade 3 AE recurs after 4 weeks but is not believed to be related to study drug, the management scheme outlined above may be repeated.

Participants experiencing Grade 3 or greater AEs (requiring permanent discontinuation of study drug) should be followed closely for resolution of the AE to Grade  $\leq 2$ , and [name] must be consulted.

Participants with Grade 3 asymptomatic laboratory abnormalities in cholesterol, triglycerides or bilirubin (if on atazanavir) may continue study drug.

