### **8.3 Early Discontinuation**

Any participant who develops a Grade 3 or 4 symptom or laboratory abnormality (other than bilirubin, cholesterol and triglycerides, UNLESS THE INVESTIGATOR HAS A COMPELLING REASON TO THINK IT IS NOT RELATED TO STUDY DRUG) will be evaluated and will have study treatment withheld until the toxicity resolves ( $\leq$  Grade 2). If the abnormality is thought to be related to study treatment, the participant will not be rechallenged without discussion with [name] (see Section 7.2). Participants who have to discontinue study drug early (for the above listed reasons or confirmed virologic failure) but have been on study drug for at least 12 weeks will undergo a final safety evaluation, blood draw for stored serum and plasma, DXA scan and FibroScan. All participants will remain in follow-up for resolution of Grade 3 or 4 toxicities.

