## 9.3 Primary Endpoint Assessments

The safety (frequency of maintaining HIV-1 RNA <50 copies/mL) and tolerability (frequency of study drug discontinuation due to study-drug related AEs and frequency of study-drug related ≥ Grade 3 lab or clinical events whether or not study drug was discontinued) of bictegravir + tenofovir alafenamide + emtricitabine in HIV-infected TW on female hormone therapy vs continued ART.

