## 9.5 Study Monitoring

This is an open label study. Accrual and a summary of all Grade ≥2 signs and symptoms and all Grade ≥3 laboratory abnormalities will be prepared by the central data management site at the McGovern School of Medicine, and reviewed by the study team monthly. The AE summary will be divided by treatment arms and reviewed regularly by the team, as will baseline characteristics, early treatment discontinuations, and study discontinuations. The data management center at the McGovern School of Medicine will also prepare a quarterly report of all AEs by treatment arm to be reviewed by the team.

Approximately six-nine months after enrollment of the first participant, an interim review of the study will occur. An independent Study Monitoring Committee (SMC) comprised of three HIV investigators not involved in the study will review accrual, AE summaries, off-treatment, and off-study rates broken down by randomized

treatment arm. A SMC may also be convened if a reason is identified by the study team, the data management center, or in consultation with the sponsor.

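### Safety labs are not scheduled between Weeks 12 and 48, so silent Grade 3 or higher blood-count, liver or creatinine events confined to that interval escape the primary tolerability endpoint

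*Combined protocol and SAP*

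**What the plan says.** The footnote to the table in Section 6.1 defines the panel: "Safety labs include: CBC with differential, chemistry panel including liver enzymes (ALT, AST, Alk Phos), total bilirubin and serum creatinine". The row is marked at screening, baseline, Weeks 4, 12 and 48, and early discontinuation, and is empty at Weeks 24 and 36. Participants attend both of those visits for a targeted exam and dispensing. At Week 24 they also give blood for HIV-1 RNA, CD4 count, fasting lipids and banked samples. No blood draw is marked at Week 36.

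No other section fills the gap. Section 6.6 adds glucose to the Week 24 fasting tests, keeps the banked samples for metabolic and inflammatory markers, and lists the safety panel without timing. Its recording rule, "For post-entry assessments, record all laboratory values for WBC, Hb, platelet, glucose, creatinine, AST, ALT, lipid profile", says what goes on the CRF but orders no test.

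Three other parts of the plan depend on these results:

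- **Primary endpoint (9.3).** Tolerability includes the "frequency of study-drug related ≥ Grade 3 lab or clinical events whether or not study drug was discontinued". Section 9.6.2 reports treatment-related AEs through Week 48.
- **Withholding rules (7.0, 7.2, 8.3).** Mandated management "will be mandated only for toxicities attributable to study drug (for Arm A participants"). Under 7.2, a participant with a Grade 3 event "should have all antiretroviral medications, including study drug, withheld unless the investigator has compelling evidence" of another cause. Section 8.3 applies to "Any participant who develops a Grade 3 or 4 symptom or laboratory abnormality (other than bilirubin, cholesterol and triglycerides").
- **Interim review (9.5).** "Approximately six-nine months after enrollment of the first participant, an interim review of the study will occur".

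**The concern.** The endpoint covers 48 weeks, but the tests that feed much of its laboratory part stop at Week 12 and resume at Week 48. A study-drug related Grade 3 or higher abnormality in blood counts, liver enzymes, bilirubin or creatinine is not counted if it begins after the Week 12 draw, causes no symptoms, prompts no unscheduled test and resolves before Week 48.

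There are two consequences. First, the absolute count in the laboratory part of the primary endpoint may be too low. In an arm of 24, one participant is 1/24 = 4.2 percentage points. Second, in Arm A, where the withholding rules apply, nobody can act on an abnormality that has not been measured. This second point concerns blood counts, ALT, AST, alkaline phosphatase and creatinine. Bilirubin is exempt under 8.3 (7.2 exempts it only on atazanavir).

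The existing safeguards do not close the gap. Recording of symptoms, signs and diagnoses at each visit cannot find a silent change. The monthly review of Grade 3 or higher labs and the quarterly reports show only tests that were done.

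**Working it through.** The plan gives no event rate, onset pattern or duration for such events, and no figure of its own on this point to reproduce. The schedule arithmetic below is firm; the detection figures rest on stated assumptions.

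**Length of the gap.** 48 − 12 = 36 weeks, and 36/48 = 75% of treatment time. Section 6.2 states: "Visit windows for all subsequent visits will be +/- 14 days from the expected date". With those windows the gap runs from 46 − 14 = 32 weeks to 50 − 10 = 40 weeks.

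**Interim review.** Six months is 26.1 weeks and nine months 39.1 weeks after first enrollment. The earliest possible Week 48 visit is at Week 46. The review therefore has no scheduled results for these analytes after Week 12, apart from early-discontinuation labs.

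**Chance of detection.** An event with onset t and duration D is caught if a draw falls in [t, t + D]. Draws are at Weeks 4, 12 and 48, with or without Week 24, at nominal times and with no unscheduled tests. Onset is one of:

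- uniform on 0 to 48 weeks;
- exponential with mean m = 8 or 4 weeks, truncated at 48, so that P(a < t < b) = (e^(−a/m) − e^(−b/m)) / (1 − e^(−48/m)).

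Example, D = 4: the catching onsets are 0–4, 8–12 and 44–48, so 12/48 = 25%. Week 24 adds 20–24, giving 16/48 = 33%. With mean 8, that added stretch is worth (e^(−2.5) − e^(−3)) / (1 − e^(−6)) = 3.2 points.

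| Duration (weeks) | Uniform: now → with Week 24 (gain) | Mean 8: now → with Week 24 (gain) | Mean 4: gain |
|---|---|---|---|
| 4 | 12/48 = 25% → 16/48 = 33% (8) | 54.1% → 57.4% (3.2) | 0.4 |
| 8 | 20/48 = 42% → 28/48 = 58% (17) | 78.3% → 86.9% (8.6) | 1.6 |
| 12 | 24/48 = 50% → 36/48 = 75% (25) | 78.7% → 96.1% (17.4) | 4.7 |
| 24 | 36/48 = 75% → 100% (25) | 82.6% → 100% (17.4) | 4.7 |
| 36 | 100% → 100% (0) | 100% → 100% (0) | 0 |

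**Share of all events lost in the Week 12 to 48 gap.** These are onsets between Week 12 and Week 48 − D. Under uniform onset the share is (36 − D)/48, that is 66.7%, 58.3%, 50% and 25% for D = 4, 8, 12 and 24. With mean 8 it is 22.0%, 21.7%, 21.3% and 17.4%. With mean 4 it is about 5% throughout.

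**In participants.** Events lost = 24 × true rate × share lost; events recovered by Week 24 = 24 × true rate × gain. The 24 is Arm A as enrolled. Ranges run over D = 4 to 24.

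| Onset | Lost, rate 2% | Lost, rate 10% | Recovered, rate 2% | Recovered, rate 10% |
|---|---|---|---|---|
| Uniform | 0.12–0.32 | 0.6–1.6 | 0.04–0.12 | 0.2–0.6 |
| Mean 8 weeks | 0.08–0.11 | 0.42–0.53 | 0.02–0.08 | 0.08–0.42 |
| Mean 4 weeks | 0.02 | 0.11–0.12 | 0.002–0.02 | 0.01–0.11 |

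At a 6% rate the largest loss is 24 × 0.06 × 0.667 = 0.96, so the loss stays below one participant in every scenario up to that rate.

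**What Week 24 leaves uncaught.** Among events with uniform onset after Week 12, the share missed falls from 89%, 78%, 67% and 33% to 78%, 56%, 33% and 0% for D = 4, 8, 12 and 24.

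**The case against.** The strongest reply is that every finite schedule misses silent events that start and end between two draws, and that the same would be true of Weeks 24 to 48 after the change. Draws at Weeks 4 and 12 after a switch are a defensible front-loaded design. The regimen is commercially available (5.3), entrants may already take TAF with FTC (4.1.5), and those with poor baseline laboratory values are excluded (4.2.6). Section 2.1 reports no BIC discontinuations for adverse events or clinically significant laboratory abnormalities in Phase II. The study is a pilot with exploratory analysis, and if onset is very early the loss is about 0.02 to 0.12 of a participant. The change also does little for the interim review: at six to nine months, only participants enrolled in about the first 2 to 15 weeks would have a Week 24 panel.

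Most of this stands as a limit on size. It does not remove the gap. Loss above one participant needs both roughly uniform onset and a rate above 6%. The Phase II reassurance is weak for Weeks 12 to 48, because the studies cited for it are titled as 10-day monotherapy. Section 2.1 itself says there are no tolerability data for this regimen in this population. Nothing in 9.3 restricts events to scheduled draws, so unscheduled tests may find some, but the protocol does not require them.

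**Conclusion.** The concern holds. The 36-week gap is certain from Section 6.1 and affects the laboratory part of the primary tolerability endpoint. Its numerical effect cannot be derived from the documents. Under the assumptions above it is most likely a fraction of one Arm A participant, and at most 1.6. It is zero for abnormalities lasting 36 weeks or more, which a scheduled draw will meet.

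The effect is under-counting and possible delay in acting on a silent abnormality. Both arms have the same schedule, so no between-arm bias is claimed. The Week 48 AST, ALT and eGFR comparisons are unaffected. This is a change the sponsor should make because it is cheap and serves the primary objective; the trial is not invalid without it.

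**What to change.** Mark the safety-lab row at Week 24 in Section 6.1, for both arms, using the fasting draw already taken at that visit. The longest interval without the panel falls from 36 to 24 weeks. Week 36 is not proposed, because no blood is drawn there and it would add a procedure. The protocol could also note that the Week 24 to 48 interval remains, and that clinically indicated unscheduled results count toward 9.3.

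The cost is at most 48 local CBC and chemistry panels, or about 40 if the planned attrition occurs (20 per arm × 2). No new visit is needed, and Section 6.6 already requires post-entry WBC, Hb, platelet, creatinine, AST and ALT values on the CRF.

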## 6.2 Timing of Study Evaluations

TW  $\geq 18$  years of age will be recruited from the Thomas Street Health Center (TSHC, the Harris Health HIV clinic) and community service organizations serving HIV-infected TW.

### Visit 1 Screening

After obtaining informed consent, participants will undergo a series of screening evaluations to determine eligibility (see Section 6.1). If needed, medical records will be requested from the participant's primary physician to confirm eligibility. If eligible, the subject will undergo whole body DXA and FibroScan performance. DXA images will be sent to the reading centers in electronic format. FibroScan data will be interpreted by [name] and housed locally. Imaging procedures will not be scheduled until eligibility is confirmed by physical exam, medical history and laboratory parameters.

### Visit 2 Baseline (within 45 days of screening)

Once eligibility has been confirmed, the subject will be randomized 1: 1 to either:

ARM A: Immediate switch of current ART to bictegravir + tenofovir alafenamide + emtricitabine for 48 weeks.  
or

ARM B: Continue current ART unchanged for 48 weeks.

Visit windows for all subsequent visits will be +/- 14 days from the expected date.

### Week 48 Visit

At this visit, participants will be referred to their primary provider to determine the best ART regimen for them to continue on off-study.

### Discontinuation Visit

A discontinuation visit should occur for any participant who has completed 12 or more weeks of study drug.

## 6.3 Pregnancy

Not applicable since no participant will be capable of becoming pregnant.

## 6.4 Discontinuation Evaluations

### Evaluations for Randomized or Registered Participants Who Do Not Start Study Treatment

Participants who do not start study treatment will be taken off study with no further evaluations required. The subject will be replaced. All case report forms (CRFs) must be completed and keyed for the period up to and including week 0.

### Premature Study Treatment/Background ART Discontinuation Evaluations

Participants who discontinue study drug due to an AE will be followed on-study off drug. The subject will complete all study evaluations and then be taken off study.

Participants who discontinue study drug for  $\geq 14$  days or who have confirmed virologic failure (two measurements  $> 200$  copies/mL) will complete the Discontinuation Visit evaluations and then be taken off study.

Similarly, participants randomized to Arm B who discontinue their entry ART regimen for  $\geq 14$  consecutive days will complete the Discontinuation Visit evaluations will and then be taken off study.

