### **7.3 Grade 4 Toxicity**

Participants who develop a Grade 4 symptomatic AE or toxicity will have study drug discontinued. If the site investigator has compelling evidence that the AE has not been caused by the study drug, dosing may resume when the AE has resolved and after consulting [name]. Participants experiencing Grade 4 AEs requiring permanent discontinuation of study drug should be followed closely until resolution of the AE to Grade  $\leq 2$ , and [name] must be consulted.

Participants with Grade 4 asymptomatic laboratory abnormalities in cholesterol or triglycerides may continue study drug.

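### Section 6.4 gives two incompatible follow-up rules for an AE-related stop of 14 days or more; one of them ends collection of HIV-1 RNA that the supplementary ITT analysis needs

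*Combined protocol and SAP*

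**What the plan says.** The part of section 6.4 on premature discontinuation has three paragraphs.

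- Paragraph 1 deals with stops caused by an AE: "Participants who discontinue study drug due to an AE will be followed on-study off drug. The subject will complete all study evaluations". Only after that does the participant leave the study.
- Paragraph 2 deals with study drug stopped for 14 days or more, or confirmed virologic failure. These participants "will complete the Discontinuation Visit evaluations and then be taken off study". It names no reason for the stop and makes no exception for AEs.
- Paragraph 3 covers the control arm. It begins "Similarly, participants randomized to Arm B who discontinue their entry ART regimen for" 14 consecutive days or more, and ends as paragraph 2 does. It has no AE provision.

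Three other sections bear on which rule governs. In 6.2: "A discontinuation visit should occur for any participant who has completed 12 or more weeks of study drug". Section 8.3 says that those who stop early for toxicity or virologic failure but "have been on study drug for at least 12 weeks will undergo a final safety evaluation", with stored blood, DXA and FibroScan, and adds: "All participants will remain in follow-up for resolution of Grade 3 or 4 toxicities". Section 8.2, which lists reasons for leaving the study, includes neither toxicity nor a 14-day stop. Both appear only in 8.1, as reasons to stop drug.

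On the analysis side, 9.3 makes maintained HIV-1 RNA below 50 copies/mL the safety endpoint. Section 9.6.1 makes the primary analysis as-treated, with data cut off at a stop of 14 or more consecutive days, and adds an ITT analysis as a supplement.

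**The concern.** A participant who permanently stops the switch regimen because of an AE falls under two instructions that cannot both be carried out. Site staff must choose, and different choices for different participants would each be defensible from the text.

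The choice matters because one branch ends data collection. The participants removed would be those who did not tolerate the regimen, so the missing HIV-1 RNA would be tied to the AE and not scattered at random. The ITT analysis is the only planned analysis that could use virologic results after a stop, and values never collected cannot be recovered later. Section 9.6.1 states no rule for missing values in that analysis, so its result for these participants would rest on a convention chosen afterwards.

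**Working it through.** The plan gives no figure on this point, so there is nothing to reproduce. The check is a comparison of texts and a count from the 6.1 schedule.

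**1. How far the two rules overlap.** Treatment runs 48 weeks, and the removal rule needs 14 days (2 weeks) off drug. A permanent AE stop reaches 14 days within the study period unless it begins after week 48 − 2 = 46. Nearly every permanent AE stop therefore meets paragraphs 1 and 2 together. Read literally, paragraph 2 would leave paragraph 1 with almost nothing to govern.

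**2. Which rule the rest of the protocol favours.**

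| Evidence | Leans towards |
|---|---|
| 6.4 paragraph 1 is specific to AEs; paragraph 2 is general | staying on study |
| 8.2 omits toxicity and 14-day stops | staying on study |
| 8.3 is also toxicity-specific, but calls for a final evaluation and then follow-up for toxicity resolution | leaving after an exit visit |
| 6.4 paragraph 3 (Arm B) has only the removal rule | no AE exception in that arm |

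The balance favours paragraph 1, but no sentence sets an order of precedence.

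**3. What is lost per participant if paragraph 2 is followed.** Inputs from 6.1: post-baseline HIV-1 RNA at weeks 4, 12, 24 and 48 (4 values); safety labs at weeks 4, 12 and 48 (3 sets). The Early Discontinuation column adds at most one of each.

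| Taken off study | Scheduled HIV-1 RNA not collected | Net of one exit value | Safety-lab sets not collected |
|---|---|---|---|
| Before week 4 | 4 of 4 | 4 − 1 = 3 | 3 of 3 |
| Weeks 4–12 | 3 of 4 | 3 − 1 = 2 | 2 of 3 |
| Weeks 12–24 | 2 of 4 | 2 − 1 = 1 | 1 of 3 |
| Weeks 24–48 | 1 of 4 | 1 − 1 = 0 | 1 of 3 |

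The Week 48 value is missing in every row, because an exit value is taken earlier. Whether the first two rows receive an exit value is itself unclear. Paragraph 2 sets no minimum time on drug, while 6.2 and 8.3 specify the visit only after at least 12 weeks. Under paragraph 1 the loss is 0 in every row.

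**4. Which analyses are touched.** The as-treated primary analysis discards data after a 14-day stop in any case, so it is the same under either rule. The AE that led to the stop still counts towards the tolerability part of 9.3. The ITT analysis of the virologic endpoint is affected.

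**5. Illustration under assumed counts.** The documents give no rate of AE stops in this trial. Suppose that k of the 24 Arm A participants stop for an AE and are taken off study, that all others are suppressed, and that the endpoint is read at Week 48. Observed values alone give (24 − k)/(24 − k) = 100%. Counting missing as failure gives (24 − k)/24:

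- k = 1: 23/24 = 95.8%
- k = 2: 22/24 = 91.7%
- k = 3: 21/24 = 87.5%
- k = 4: 20/24 = 83.3%

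The gap shows how far the ITT result could depend on an unstated convention. It does not estimate a bias.

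**The case against.** The strongest reply is that ordinary reading resolves the overlap. A specific rule prevails over a general one, paragraph 1 would be nearly idle otherwise, and 8.2 agrees. Harm then needs both a long AE stop and staff who choose paragraph 2. Even so, it reaches only a supplementary analysis in a 48-person pilot that 9.6 declares exploratory. Section 2.1 reports no Phase II discontinuations of bictegravir for AEs, which points to few cases. Section 9.6.3 and the monitoring committee review would show discontinuations and off-study rates by arm. Most of this stands and limits the severity. It does not remove the conflict, because 8.3 is equally specific to toxicity and leans the other way.

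A reader might infer four stronger claims that the documents do not support.

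- *Toxicity holds lead to removal, and only in Arm A.* Section 7.2 says of a resolved Grade 3 event "at which time study drug may be reintroduced at the discretion of" the study chair. Sections 6.5 and 7.0 list interruptions separately from discontinuation, and 8.1 is titled as covering permanent stops. The better reading is that a hold ending in restart is not a discontinuation. Section 7.3 blurs this by calling a stop a discontinuation and then allowing that "dosing may resume when the AE has resolved and after consulting" the chair. That is loose wording and does not establish a differential loss.
- *An early stopper leaves with no HIV-1 RNA at all.* Paragraph 2 requires the exit evaluations without a 12-week limit, so total loss is a worst case.
- *Related AEs go unreported after removal.* Section 8.3 follows Grade 3 or 4 toxicities to resolution, and 10.4 extends SAE reporting to four weeks after the last dose. No material gap is shown.
- *The primary comparison is biased.* The as-treated cut-off is a declared choice that this conflict does not alter.

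**Conclusion.** The conflict within 6.4 is real and unresolved elsewhere in the protocol; confidence in that reading is high. Its consequence is conditional on the removal rule being applied to AE stops. The supplementary ITT analysis would then lose later HIV-1 RNA, always including Week 48, for participants selected by an AE. How many would be affected, and in which direction the arm comparison would move, cannot be derived from the documents; the number is probably small. Severity is minor: a clarification worth making because uncollected data cannot be restored and the remedy is cheap.

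**What to change.** 1. In 6.4, state that paragraph 1 governs every AE-related stop, whatever its length, so that these participants complete the scheduled evaluations through Week 48. Limit paragraph 2 to stops not due to an AE and to confirmed virologic failure.
2. Apply the same rule to Arm B participants who stop entry ART for an AE. Paragraph 3 is clear as written, so this is an alignment and not a correction. Without it, settling paragraph 1 for Arm A would make follow-up differ by arm.
3. In 9.6.1, say that HIV-1 RNA collected after such a stop enters the ITT analysis. Leave the as-treated cut-off unchanged.
4. Clerical: 8.1 cites 7.1 for toxicity requiring a permanent stop, but 7.1 covers Grade 1 or 2 events, for which drug may continue. It should cite 7.2 and 7.3.

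Toxicity holds need not be redefined for this purpose. If the sponsor chooses to define them, 8.1 and 9.6.1 should share one definition of a 14-day discontinuation, because both use that criterion.

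The cost is wording in three sections. No visit is added beyond the 6.1 schedule and no new CRF field is needed, since 6.5 already records interruptions and modifications. Two limits remain: some scheduled visits will be attended off drug, and participants who stop for non-AE reasons or have virologic failure will still leave early, so the ITT gap is narrowed and not closed.
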